**9.4 Statistical Methods**

**9.4.1 General Approach**

Descriptive statistics including the number of observations, mean, standard deviation, median, minimum, and maximum will be presented for continuous variables. Frequency and percentage of patients will be presented for categorical variables. Continuous variables will be analyzed using analysis of variance (ANOVA) or analysis of covariance (ANCOVA). Categorical variables will be analyzed using a Cochran-Mantel-Haenszel (CMH) test or a Pearson's Chi-square test.

Safety analyses will be performed on all patients enrolled in this study, while efficacy analyses will be performed only on those patients who are randomized to receive tenapanor

in the 26-week treatment period (i.e., patients treated with active control will not be included in any efficacy analyses).

#### 9.4.2 Baseline Descriptive Statistics

Baseline characteristics, including demographics, disease characteristics, prior/concomitant medications, and medical/surgical history will be summarized by treatment (including dose, if applicable) group and overall for each analysis set. These summaries will be provided for each study period separately.

#### 9.4.3 Primary Efficacy Analysis

The primary efficacy variable is the change in s-P from the end of the 26-week treatment period (Visit 13) to the end of the 12-week randomized withdrawal period (Visit 19) or the endpoint visit for this period. An endpoint visit is defined as the last visit with an s-P assessment during the randomized withdrawal period. The primary interest of this study is the difference between the tenapanor treatment and placebo treatment group in the mean change (w.r.t. the primary efficacy variable) in the responder population (the efficacy analysis set). A responder is a patient that had a serum phosphorus decrease of  $\geq 1.2$  mg/dL from enrollment (Day 1) to the end of the 26-week treatment period (Visit 13). The primary efficacy variable will be analyzed using an ANCOVA model. The model includes fixed effects for treatment, pooled investigator site, and the baseline s-P value as a continuous covariate. The baseline for this analysis is defined as the s-P value at the end of 26-week treatment period. Within the framework of this model, the difference between the tenapanor treatment and placebo treatment in the mean change from the end of the 26-week treatment period to the end of the 12-week randomized withdrawal period (or the endpoint visit for this period) will be estimated. The corresponding two-sided 95% CI and the p-value for the treatment difference will also be presented. Statistical significance will be declared if the estimated difference between the tenapanor treatment and placebo treatment in the mean change is negative (i.e.,  $< 0$ ) and the corresponding two-sided p-value is  $\leq 0.05$ .

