11. For enrollment in the study, patients must have serum phosphorus levels of at least 6.0 mg/dL but not more than 10.0 mg/dL and have had an increase of at least 1.5 mg/dL versus pre wash-out value after 1, 2 or 3 weeks wash-out of phosphate binders.
12. Able to understand and comply with the protocol.

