#### **7.4 Efficacy Variables**

Serum phosphorus will be measured at all study visits. The primary efficacy variable will be the change in s-P from the end of the 26-week treatment period (Visit 13) to the end of the randomized withdrawal period or the endpoint visit for this period. The primary efficacy analysis will be based on the difference between the tenapanor treatment and placebo treatment group in the responder population. A responder is a patient that had a serum phosphorus decrease of  $\geq 1.2$  mg/dL from enrollment (Day 1) to the end of the 26-week treatment period (Visit 13).

The following are the secondary variables:

- Patients reaching serum phosphorus goal levels defined as  $< 5.5$  mg/dL during the 26-week treatment period
- Ca x P product
- iFGF23 (intact) and cFGF23 (c-terminus)
- Kidney Disease and Quality of Life survey (KDQOL)
  - Kidney Disease and Quality of Life™ (KDQOL™-36) (Copyright © 2000 by RAND and the University of Arizona)
- Dialysis Symptom Index survey (DSI)
  - The University of Pittsburgh Medical Center, VA Pittsburgh Healthcare System (Weisbord et al. J Pain Symptom Manage, 2004:27, 226-40.)

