### **9.2 Determination of Sample Size**

Approximately five hundred sixty (560) male and female patients with end stage renal disease (ESRD) on chronic maintenance hemodialysis (HD) 3 times a week for a minimum of 3 months or peritoneal dialysis (PD) for a minimum of 6 months will be enrolled in this study. Patients will be randomized in a 3:1 ratio to receive either tenapanor (~420 patients) or active control (~140 patients). Those patients in the tenapanor group will be randomized at the end of the 26-week treatment period to enter into the randomized withdrawal period to either remain on their current dose of tenapanor or placebo in a 1:1 ratio.

For the primary efficacy analysis, a sample size of 146 patients (73 patients/group) in the 12-week randomized withdrawal period is expected to provide more than 95% power to detect a difference between tenapanor and placebo treatment in the change in serum phosphorus from the end of the 26-week treatment period to the end of the 12-week randomized withdrawal period or the endpoint visit for this period, between the tenapanor treatment and placebo. This calculation is based on a two-sample t-test with a two-sided significance level of  $\alpha=0.05$ , an assumed treatment difference of 1.0 mg/dL and a common standard deviation of 1.6 mg/dL. This sample size (560) allows for a 30% dropout rate, meaning 30% of patients will not complete the 26-week treatment period. This sample size also assumes at least 50% of patients in the tenapanor group will be considered responders in the 26-week treatment period, i.e., patients who achieves at least a 1.2 mg/dL reduction from baseline to the end of the 26-week treatment period.

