To support the primary efficacy analysis (LOCF method), a sensitivity analysis will be performed using a mixed-effects model for repeated measures (MMRM). Specifically, the dependent variable for the MMRM model will be the change in s-P from the end of the 26-week treatment period (Visit 13) to each visit during the 12-week randomized withdrawal period, and the MMRM model includes fixed effects of treatment, pooled investigator site, visit (Visit 14 through Visit 19), treatment-by-visit interaction, and the baseline s-P value as a continuous covariate. The baseline is defined as the s-P value at the end of 26-week treatment period. The covariance matrix for the repeated measures will be assumed to be unstructured. Within the framework of this model, the difference between the tenapanor treatment and placebo treatment in the mean change from the end of the 26-week treatment period to week-12 of the 12-week randomized withdrawal period will be estimated. The corresponding two-sided 95% CI and the p-value for the treatment difference will also be presented.

An endpoint visit (the LOCF method) will also be used for other efficacy analyses, if applicable. All other efficacy analyses will be performed based on the observed data.

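### The primary ANCOVA and its companion analyses do not adjust for untreated Day 1 s-P; adding it is a minor, optional gain in precision

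*Combined protocol and SAP*

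**What the plan says.** Section 9.4.3 gives the primary model: "The model includes fixed effects for treatment, pooled investigator site, and the baseline s-P value as a continuous covariate". It then identifies the covariate: "The baseline for this analysis is defined as the s-P value at the end of 26-week treatment period". Section 9.4.4.1 applies the same method to the ITT set and to the individual-dose comparisons. The MMRM in Section 9.4.5 ends its list of fixed effects with "treatment-by-visit interaction, and the baseline s-P value as a continuous covariate", and its baseline is again the Visit 13 value.

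Day 1 s-P is available. Section 7.4 states: "Serum phosphorus will be measured at all study visits". The Schedule of Events marks s-P at Visit 5, and Section 8.3 lists pre-dialysis laboratory tests at that visit. The patient is then off binders: Section 5.1 requires patients to "have had an increase of at least 1.5 mg/dL versus pre wash-out value after 1, 2 or 3 weeks wash-out of phosphate binders". Sections 7.4 and 9.4.3 define a responder by a fall of at least 1.2 mg/dL from Day 1 to Visit 13, so the value is needed to classify every patient in the efficacy analysis set.

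On size, Section 9.2 says "This calculation is based on a two-sample t-test with a two-sided significance level of" 0.05. It assumes a difference of 1.0 mg/dL, an SD of 1.6 mg/dL and 73 patients per group, and states power above 95%.

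**The concern.** The endpoint is how far s-P moves after Visit 13. A patient switched to placebo should drift back toward the untreated level, and Day 1 is a reading of that level. Visit 13 is a single on-drug reading that mixes untreated level, drug response and measurement noise. Day 1 may therefore explain part of the outcome that Visit 13 does not, mainly on placebo. In the tenapanor arm it may help a little by offsetting noise in the Visit 13 reading.

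Day 1 is fixed before the second randomization, so prespecified adjustment for it is valid. What is at stake is precision only: the width of the confidence interval, and some power in the key secondary tests. The individual-dose comparisons use only part of the sample.

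**Working it through.** **1. The plan's own figure.** Inputs from Section 9.2: 73 per group, difference 1.0, SD 1.6, two-sided alpha 0.05.
- SE = 1.6 × √(2/73) = 0.265, and noncentrality = 1.0/0.265 = 3.78.
- With 144 degrees of freedom the noncentral t gives power of 96.3%, so the stated figure of more than 95% reproduces.
- Expected responders: 560 × 0.75 × 0.70 × 0.50 = 147, against 146 needed.

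**2. Effect of a second covariate.** Let r be the partial correlation of Day 1 s-P with the change, given treatment, site and Visit 13 s-P. Take 1.6 as the residual SD of the planned model (an assumption, since Section 9.2 uses an unadjusted t-test). Then new SD = 1.6 × √(1 − r²), and the fall in residual variance is r². The documents do not give r, so a range is shown.

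| Fall in variance (r²) | Residual SD | Power | 95% CI half-width (mg/dL) |
|---|---|---|---|
| 0% | 1.600 | 96.3% | 0.523 |
| 1% | 1.592 | 96.5% | 0.521 |
| 2% | 1.584 | 96.6% | 0.518 |
| 4% | 1.568 | 96.9% | 0.513 |
| 7% | 1.543 | 97.3% | 0.505 |

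In patients, a fall of 2% is worth 146 × (1/0.98 − 1) ≈ 3, and a fall of 7% is worth 146 × (1/0.93 − 1) ≈ 11.

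**3. Cost.** The number of pooled sites is not stated. With about 12 model parameters assumed, 146 − 12 = 134 residual degrees of freedom remain. One more parameter costs about 1/134 ≈ 0.7% of variance, so break-even is at r ≈ √(1/134) ≈ 0.09.

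**4. What r is plausible.** Responders were simulated with the 6.0-10.0 mg/dL entry window, the 1.2 mg/dL responder cut, one common slope, and drift in each patient's untreated level. All variance components are assumed. Fall in variance = 1 − (SD with / SD without)².

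| Between-patient SD | Within-patient SD | Drift SD | Residual SD without Day 1 | Residual SD with Day 1 | Fall in variance |
|---|---|---|---|---|---|
| 1.4 | 0.6 | 0.4 | 0.961 | 0.919 | 8.5% |
| 1.2 | 0.8 | 0.5 | 1.150 | 1.122 | 4.8% |
| 1.0 | 1.0 | 0.8 | 1.439 | 1.426 | 1.8% |
| 0.7 | 1.1 | 1.0 | 1.598 | 1.593 | 0.6% |
| 0.5 | 1.2 | 1.0 | 1.674 | 1.673 | 0.1% |
| 0.3 | 1.3 | 1.0 | 1.753 | 1.753 | 0.0% |

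Partial r was 0.02-0.47 on placebo and 0.01-0.13 on tenapanor. The largest gain arises at a residual SD of 0.96, far below the planned 1.6, so it should not be applied to the planned figures.

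Further runs without drift (between-patient SD 0.8-1.1, within-patient SD 0.8-1.2) gave falls of about 2-7%. Adding drift brought this to about 1-3%. Where the residual SD was near 1.6, the fall was about 1-2%. Without the responder cut, as in the ITT set, falls ranged from about 1% to 12% across runs.

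**The case against.** The strongest reply is that nothing is wrong with the plan. The ANCOVA already adjusts for the baseline of the randomized period. Leaving out a second covariate does not bias a randomized comparison, and planned power is above 95% either way. All of that stands.

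It is also fair that no figure in the documents shows Day 1 to be prognostic once Visit 13 is in the model. Three features limit what it can add:
- Entry rules narrow its spread: "patients must have serum phosphorus levels of at least 6.0 mg/dL but not more than 10.0 mg/dL".
- The responder cut ties Day 1 to Visit 13 (correlation 0.50-0.73 in the simulations), so part of its information is already used.
- Prediction is expected mainly on placebo, while the model fits one common slope.

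Day 1 is also a single reading after a wash-out of variable length, so it is not an exact measure of the untreated level. The range must therefore reach zero.

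A reader might infer two stronger claims, and the documents support neither:
- **That Day 1 makes missing-at-random more credible for patients stopped at s-P ≥9 mg/dL.** Under Section 5.4 the stop is triggered by a measured s-P. When taken at a scheduled visit, that value is an outcome in the MMRM. Dropout driven by an observed outcome is already missing at random under the planned model.
- **That the change has no cost.** It costs one degree of freedom, and below r ≈ 0.09 it brings no net gain.

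Finally, Section 9.1 says a separate SAP governs. Its text is not in the document reviewed, so whether it already includes Day 1 cannot be checked, although Section 9.1 expects no changes to the primary analysis.

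**Conclusion.** The point holds as a minor efficiency improvement and does not identify an error. A valid covariate that is already collected and plausibly prognostic is left out of the primary ANCOVA, the same-method key secondary analyses and the MMRM.

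The likely gain in the efficacy set is about 0-7% of residual variance, and about 1-2% where the residual SD is near 1.6, before the 0.7% cost. At the planned difference and SD, power rises from 96.3% to at most about 97.3%, and the CI half-width narrows from 0.523 to no less than about 0.505 mg/dL. The ITT set may gain more. These sizes rest on assumed variance components, because the documents report no Day 1 correlation. The plan's sample size and stated power are unaffected.

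**What to change.** Before unblinding, prespecify Day 1 s-P as a second continuous covariate, beside Visit 13 s-P, in Section 9.4.3, in the key secondary analyses of Section 9.4.4.1 and in the MMRM of Section 9.4.5. Because ITT membership does not depend on responder status, confirm that Day 1 s-P is present for ITT patients and state how a missing value would be handled. If the separate SAP already includes Day 1, align Section 9.4.3 with it.

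The cost is a wording change and one degree of freedom. No new data, visits or patients are needed.

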#### 9.4.4 Secondary Efficacy Analyses

##### 9.4.4.1 Key Secondary Efficacy Analyses

The analysis method described for the primary efficacy variable in [Section 9.4.3](#) will be performed as follows:

- in the ITT analysis set
- to compare the individual doses of tenapanor and placebo in the ITT analysis set – from high dose to low dose
- to compare the individual doses of tenapanor and placebo in the efficacy analysis set – from high dose to low dose

A sequential testing procedure will be used to control the family-wise type I error rate associated with the key secondary efficacy analyses. Specifically, the primary efficacy analysis will be performed at the 5% significance level. If statistical significance is declared for this analysis, then the first key secondary efficacy analysis listed in this section will be performed at the 5% level. If statistical significance is declared for this analysis, then the next key secondary efficacy analysis will be performed at the 5% level. This procedure continues until one of the key secondary efficacy analysis in the list results in a p-value >5%. Statistical significance will be declared for secondary efficacy analyses up to this point in the list.

#### 9.4.4.2 Other Secondary Efficacy Analyses

The change in s-P from baseline to the end of 26-week treatment period will be analyzed using an ANCOVA model with effects for pooled investigator site, and the baseline s-P value as a continuous covariate. The LS-mean of the change will be presented with the corresponding two-sided 95% CI and p-value.

The proportion of patients reaching serum phosphorus goal levels of <5.5 mg/dl at each visit during the 26-week treatment period will be estimated with asymptotic 95% CI.

ANCOVA will be performed for the change from baseline at each visit for the following variables:

- Ca x P product
- iFGF23 (intact) and cFGF23 (c-terminus), both on a logarithmic scale
- Kidney Disease Quality of Life survey (KDQoL)
- Dialysis Symptom Index survey (DSI)

The ANCOVA model includes fixed effects for treatment (including dose, if applicable) group, pooled investigator site, and the baseline value (defined for the individual study period) as a continuous covariate. Specifically,

- for the 26-week treatment period and safety extension period, the LS-mean of the change will be presented with the corresponding two-sided 95% CI and p-value. For iFGF23 and cFGF23, the back-transformed point estimate and 95% CI will be provided.
- for the randomized withdrawal period, the treatment group difference between tenapanor and placebo in the mean change will be estimated with the corresponding two-sided 95% CI and p-value. For iFGF23 and cFGF23, the back-transformed point estimate and 95% CI will be provided.

All secondary efficacy analyses described in this section will be descriptive and no multiplicity adjustment will be made for these analyses.

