**Efficacy analyses:**

All efficacy variables will be summarized by treatment (including dose, if applicable) group, using descriptive statistics. All continuous efficacy variables (s-P, Ca x P, iFGF23, cFGF23, KDQoL and DSI) will be analyzed using an analysis of covariance (ANCOVA) model with terms for pooled investigator site, treatment (including dose, if

applicable), and baseline as the covariable. The change from baseline will be the dependent variable. The least squares means (LSmeans) will be presented for the change from baseline values for each treatment group (including dose, if applicable) with the 95% confidence interval (CI).

The primary efficacy variable will be the change in serum phosphorus from the end of the 26-week treatment period to the end of the 12-week randomized withdrawal period or the endpoint visit for this period. The primary efficacy analysis will be based on the difference between the tenapanor treatment and placebo treatment group in the responder population (efficacy analysis set). Endpoint for this analysis is defined as the last serum phosphorus lab value assessment during and up to the end of the 12-week randomized withdrawal period.

Secondary analyses are described in [Section 9](#) and are detailed in the statistical analysis plan (SAP).

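### The 26-week and extension efficacy results are single-arm LS-mean changes, and the usual ANCOVA standard error understates their uncertainty as estimates of the population mean change

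*Combined protocol and SAP*

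**What the plan says.** Section 9.4.1 (General Approach) limits the efficacy population: "efficacy analyses will be performed only on those patients who are randomized to receive tenapanor" in the 26-week period. It adds that "patients treated with active control will not be included in any efficacy analyses".

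Section 9.4.4.2 (Other Secondary Efficacy Analyses) then gives two models.

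- The 26-week s-P change is "analyzed using an ANCOVA model with effects for pooled investigator site, and the baseline s-P value as a continuous covariate". There is no treatment or dose term. The reported result is the LS-mean itself: "The LS-mean of the change will be presented with the corresponding two-sided 95% CI and p-value".
- For Ca x P, iFGF23 and cFGF23 (log scale), KDQoL and DSI, the model also has a treatment term, with dose where applicable. The instruction is: "for the 26-week treatment period and safety extension period, the LS-mean of the change will be presented with the corresponding two-sided 95% CI and p-value". In the randomized withdrawal period, the same section reports a tenapanor-placebo difference instead.

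The Synopsis (Efficacy analyses) makes the per-group presentation general: "The least squares means (LSmeans) will be presented for the change from baseline values for each treatment group", with a 95% CI.

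On status, Section 9.4.4.2 says: "All secondary efficacy analyses described in this section will be descriptive and no multiplicity adjustment will be made for these analyses". It names no variance estimator and does not say that inference is conditional on the observed baselines. Section 9.1 refers to a separate SAP that governs where the two differ.

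**The concern.** ANCOVA earns its smaller standard error in a randomized comparison: chance baseline differences between arms are adjusted away, so the residual variance is the right one for the difference. With one group there is nothing to adjust against. The LS-mean is evaluated at the sample's own mean baseline, where it is essentially the raw mean change (exactly so with equal site pools; Section 9.4.6 aims for comparable pools). The estimate gains no information from the covariate, yet its model standard error uses only the variance left after baseline is regressed out.

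The secondary objectives in Section 3.2 ask about tenapanor's effect on change from baseline, and a reader will take the CI as one for the mean change in such patients. For that target the interval can only be too narrow or correct, never too wide. At stake are the printed precision and, where the true change is near zero, the chance of reporting a change that is not there.

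**Working it through.** **The plan's own figure.** Section 9.2 states more than 95% power for 73 per group, difference 1.0 mg/dL, SD 1.6 mg/dL. SE = 1.6 x sqrt(2/73) = 0.265; 1.0/0.265 = 3.78; 3.78 - 1.96 = 1.82, which gives 96.5% power (96.3% by noncentral t). It reproduces. The patient flow also agrees: 560 x 0.75 = 420 on tenapanor; x 0.70 = 294 completing 26 weeks; x 0.50 = 147 responders, against 146 stated. The plan gives no precision figure for the single-arm analyses.

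**Inputs for the single-arm check.**

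- n = 294, from Section 9.2 as above.
- SD 1.6 mg/dL, the only s-P SD stated. It is given for the withdrawal-period change, so its use here is borrowed.
- Baseline spread for s-P: not stated. Entry requires 6.0 to 10.0 mg/dL (inclusion criterion 11). A uniform spread over that window has SD 4/sqrt(12) = 1.15. I assume 1.15 to 1.3. The Day 1 sample is separate from the qualifying one, so the window is not a strict limit.
- Correlation rho between baseline and follow-up: not stated. I assume 0.3, 0.5 and 0.7.

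**Formulas.** Let D = Y - X be the change from baseline X to follow-up Y, with SDs sX and sY.

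- Var(D) = sX^2 + sY^2 - 2 rho sX sY
- Var(D | X) = sY^2 (1 - rho^2)
- The standard error for the population mean change is sqrt(Var(D)/n); the model reports sqrt(Var(D | X)/n).
- Their ratio is sqrt(1 - R2) = sqrt(Var(D | X)/Var(D)), never above 1. With equal SDs it is sqrt((1 + rho)/2).
- Actual two-sided error = 2 x (1 - Phi(1.96 x ratio)).

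**Example.** Baseline SD 1.3, follow-up SD 1.6, rho 0.3: Var(D) = 1.69 + 2.56 - 1.248 = 3.002; Var(D | X) = 2.56 x 0.91 = 2.330; ratio = sqrt(0.776) = 0.881; error 8.4%.

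**Results.**

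| SDs, baseline / follow-up | rho | SE ratio | Actual error | Coverage |
|---|---|---|---|---|
| Equal | 0.3 | 0.81 | 11.4% | 88.6% |
| Equal | 0.5 | 0.87 | 9.0% | 91.0% |
| Equal | 0.7 | 0.92 | 7.1% | 92.9% |
| 1.3 / 1.6 | 0.3 | 0.88 | 8.4% | 91.6% |
| 1.3 / 1.6 | 0.5 | 0.94 | 6.5% | 93.5% |
| 1.3 / 1.6 | 0.7 | 0.99 | 5.3% | 94.7% |
| 1.15 / 1.6 | 0.3 | 0.92 | 7.3% | 92.7% |
| 1.15 / 1.6 | 0.5 | 0.97 | 5.7% | 94.3% |
| 1.15 / 1.6 | 0.7 | 1.00 | 5.0% | 95.0% |

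**Simulation.** At n = 294 with equal SDs and no site terms (40,000 runs), the ANCOVA error was 11.4%, 9.0% and 7.2% for rho 0.3, 0.5 and 0.7; a one-sample t on the change gave 5.0% to 5.1%. With 12 equal site pools (number assumed) the ANCOVA figures were 11.3%, 9.1% and 7.2%, and an SE that includes baseline variation restored about 5%. With unequal pools they were 8.8%, 8.2% and 6.8%.

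**Width.** Equal SDs of 1.6 with rho 0.5 give a change SD of sqrt(2.56) = 1.6. At n = 294 the correct half-width is 1.96 x 1.6/sqrt(294) = 0.183 mg/dL; ANCOVA would print 0.866 x 0.183 = 0.158.

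**Where it does not matter.** A 1.2 mg/dL fall with change SD 1.6 and n = 294 has z = 1.2/(1.6/sqrt(294)) = 12.9, so significance is safe. The two-arm ANCOVA difference, simulated at n = 146, rejected at 5.1%.

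**The case against.** The strongest reply is that this is a choice of target. ANCOVA inference is conditional on the observed baselines, and for that target the interval is valid: with baselines held fixed, the simulated error was 4.6% to 5.8%. That is correct, and it rules out saying that the intervals are invalid for every purpose. But Section 9.4.4.2 does not declare that target, and the objective does not suggest it.

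Second, the size is not in the documents. A reader might infer that every one of these intervals is clearly too narrow and every test exceeds 5%, because change is strongly and negatively related to baseline. The documents report no correlation and do not support that. The error vanishes when change is uncorrelated with baseline (a slope of 1 for follow-up on baseline), and in the narrow-baseline s-P settings above it can be negligible. No entry criterion sets a range for KDQoL, DSI or FGF23, so similar SDs at both times are a reasonable assumption there, but only an assumption.

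Third, the analyses are descriptive and outside the sequential testing of Section 9.4.4.1. This limits the consequence, but a printed 95% CI should still have its stated coverage, and the issue is separate from multiplicity.

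Fourth, replacing every LS-mean by a one-sample t would be wrong. Where dose or arm terms are fitted, LS-means at a common baseline are not raw group means, and raw arm means in the withdrawal period would not subtract to the ANCOVA difference. This stands and shapes the fix.

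Finally, the protocol names no variance estimator and the separate SAP governs. The point therefore assumes default model output at the sample mean baseline.

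**Conclusion.** The point holds as a matter of stated precision. As written, Section 9.4.4.2 leads to 95% CIs and p-values that are too optimistic for the population mean change by the factor sqrt(1 - R2). Under equal SDs and correlation 0.3 to 0.7, the actual error is about 11% down to 7%. For s-P with baseline SD 1.15 to 1.3 against 1.6, it is about 7-8% at correlation 0.3, about 6% at 0.5 and about 5% at 0.7. All of these rest on assumed correlations and, for s-P, on an SD borrowed from the withdrawal period. The direction does not depend on those values.

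A reader might go further and doubt the 26-week s-P conclusion or the primary result. Neither follows: a large s-P fall remains significant, and the primary and key secondary analyses are randomized contrasts, for which the ANCOVA standard error is appropriate. The under-5.5 mg/dL proportion is not an ANCOVA mean and is also outside this point. The practical exposure is small changes, such as those in KDQoL and DSI, whose SDs and correlations the documents do not give.

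**What to change.** In Section 9.4.4.2, keep the LS-mean for the 26-week and extension periods, but compute its 95% CI and p-value with a standard error that includes baseline sampling. Either add slope^2 x baseline variance / n to the squared model SE (slope of change on baseline; n and variance taken over the patients whose baselines are averaged to set the covariate value), or bootstrap patients. Do this on the log scale for FGF23 before back-transforming.

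Apply the same to any dose-group LS-mean and to the per-arm LS-mean CIs in the Synopsis. For the 26-week s-P change, which has no treatment or dose term, a one-sample t CI for the mean change is an equivalent option; it matches the LS-mean exactly only with equal site pools. Leave the withdrawal-period ANCOVA difference unchanged.

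The cost is a sentence in the plan and a line of code. Keeping the LS-mean leaves the point estimates unchanged; the CIs become somewhat wider.
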